4.1 Primary Outcomes

4.1.1 The primary outcomes will be the following perfusion-related problems:

- Soft tissue ischemia/loss (i.e. partial and full thickness soft tissue defects identified postoperatively in clinic follow up)
- Surgical site infection (i.e. soft tissue cellulitis or abscess identified postoperatively either clinically or with wound culture)
- Delayed wound healing (manifesting as suture dehiscence and opening of an incisional wound)

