2.0 Objectives

Our aim is to evaluate and to compare the above described interventions and their effect on the incidence of PRPs in patients with breast cancer undergoing mastectomy and implant-based immediate breast reconstruction (IBR). The ability to identify, prevent and treat these PRPs can help maximize aesthetic results after breast surgery, improve patient satisfaction with both mastectomy and breast reconstruction, and reduce healthcare cost associated with mastectomy and reconstruction complications.

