5.1 Study Related Activities

Potential subjects will be identified by the physician, advanced practice provider, or research coordinator. This individual will discuss the study with the patient and answer any questions or concerns they may have. This will take place in an exam room, hospital room, or by phone depending on whether or not the patient is inpatient or a clinic patient.

Signed informed consent will be obtained from each subject who will be undergoing mastectomy with immediate breast reconstruction using breast implants during a pre-operative appointment in the General Surgery (Breast Oncology) or Plastic Surgery clinic. After the subject has been identified as meeting the inclusion criteria by the clinician or research coordinator, the study coordinator will obtain the signed informed consent. A signed copy of the consent form will be given to the subject. Once the patient has agreed to take part in the study and sign the consent form, pre-operative photos of the breast will be taken. Pregnancy tests performed 15 days apart (prior to surgery) is done as standard of care for all women of childbearing age potentially undergoing this surgery.

Twenty subjects will be randomized to each arm of the study using sealed instructions provided by the study coordinator who will inform the clinician of the arm prior to surgery. The envelopes will be filled prior to the study with envelopes containing a document indicating to which group the patient will be a part of. The envelopes will be sealed and shuffled and then labeled from subject 1 through 160.

Once the subject is randomized to an arm of the study, the operating surgeon will be informed of the arm prior to the surgery. On the day of surgery, the surgeon will decide intraoperatively whether an implant/tissue expander can be safely placed without compromising perfusion of the flap. If the surgeon determines that an implant/tissue expander cannot be safely placed, they will continue to be followed as that indicates a perfusion related problem. At that point, another envelope will be introduced into the pre-made envelopes with that subject’s assigned arm. Pictures will be take pre-

The Effect of Nitroglycerin Ointment, Fluorescent Angiography, and Incisional NPWT on Mastectomy Skin Flap Perfusion-Related Problems Comprehensive Cancer Center of Wake Forest University (CCCWFU)

PI: [name] IRB #00038262 NCT03716050 Date of Document: 05/07/2019

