8.3 Statistical Analyses

8.3.1 Estimates of all primary outcomes (Soft tissue ischemia/loss, surgical site infection, delayed wound healing) and secondary outcomes (rate of operative intervention, rate of prescribing antibiotics or admission for IV antibiotic therapy, wound care management modalities and outcomes) will be calculated. These data will provide estimates of rates for each outcome that will allow planning for future studies. The rates of the primary outcomes will be reported, along with corresponding 95% confidence intervals. With an anticipated sample size of 20 in each group, the width of the exact 95% confidence interval would be approximately +/- 22.8 if the observed rate was 50%. The table below shows the power for testing against an observed rate of 10% (the anticipated average rate in the 8 study groups) in group 1 versus 20%, 30%, 40%, and 50% in other groups with an alpha of 0.20. With group sample sizes of 20 in each of the 2 groups, the study would have 84% power to detect a difference of 30%.

Numeric Results of Tests Based on the Difference: P1 - P2

H0: P1 - P2 = 0. H1: P1 - P2 = D1 ≠ 0. Test Statistic: Z test with pooled variance

Power	N1	N2	N	Trt H1	Cntrl	Diff	Target	Actual
				P1	P2	D1	Alpha	Alpha
0.36453	20	20	40	0.10	0.20	-0.10	0.2000	0.1966
0.62930	20	20	40	0.10	0.30	-0.20	0.2000	0.2228
0.84713	20	20	40	0.10	0.40	-0.30	0.2000	0.2172
0.95746	20	20	40	0.10	0.50	-0.40	0.2000	0.1920

The table below shows the target and actual alpha and power if groups are combined to have 80 subjects in each one.

Numeric Results of Tests Based on the Difference: P1 - P2

H0: P1 - P2 = 0. H1: P1 - P2 = D1 ≠ 0. Test Statistic: Z test with pooled variance

Power	N1	N2	N	Trt H1	Cntrl	Diff	Target	Actual
				P1	P2	D1	Alpha	Alpha
0.42287	80	80	160	0.10	0.20	-0.10	0.05	0.0503
0.71633	80	80	160	0.10	0.25	-0.15	0.05	0.0518
0.90284	80	80	160	0.10	0.30	-0.20	0.05	0.0513
0.97682	80	80	160	0.10	0.35	-0.25	0.05	0.0507
0.99617	80	80	160	0.10	0.40	-0.30	0.05	0.0472

With group sample sizes of 80 in each of the 2 groups, being compared, the study would have 90% power to detect a difference of 20%.

The Effect of Nitroglycerin Ointment, Fluorescent Angiography, and Incisional NPWT on Mastectomy Skin Flap Perfusion-Related Problems Comprehensive Cancer Center of Wake Forest University (CCCWFU)

PI: [name] IRB #00038262 NCT03716050 Date of Document: 05/07/2019

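### The aim concerns the incidence of perfusion-related problems (PRPs), but the plan estimates only three component rates: no patient-level any-PRP rate, no rate for implant non-placement, and no named outcome for the 10% planning rate

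*Combined protocol and SAP*

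**What the plan says.** - **Aim (2.0 Objectives).** The interventions are to be compared on "their effect on the incidence of PRPs" in patients having mastectomy with immediate implant-based reconstruction.
- **Primary outcomes (4.1).** "The primary outcomes will be the following perfusion-related problems". Three follow: soft tissue ischemia or loss ("partial and full thickness soft tissue defects identified postoperatively in clinic follow up"), surgical site infection, and delayed wound healing ("manifesting as suture dehiscence and opening of an incisional wound"). There is no composite, no hierarchy, and no rule for a patient who has more than one.
- **Analysis (8.3.1).** A rate is planned for every outcome, with 95% confidence intervals for the primary ones: "These data will provide estimates of rates for each outcome that will allow planning for future studies".
- **Planning rate (8.3.1).** Both power tables start from 10%, which the text describes only as "the anticipated average rate in the 8 study groups" and then uses as the group 1 rate. No outcome is named.
- **Non-placement (5.1).** If the surgeon judges during the operation that an implant or expander cannot safely be placed, 5.1 says of such patients: "they will continue to be followed as that indicates a perfusion related problem". A further envelope for the same arm is then added.

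**The concern.** The aim reads most naturally as a question about patients: how many have a PRP under each regimen? The plan produces three marginal rates per arm and no count of patients with at least one. By their definitions the three problems can occur together, since one breast can have a full-thickness defect, an opened incision and an infection. The marginal rates therefore do not determine the any-PRP rate.

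Non-placement is a second gap. Section 5.1 calls it a PRP, but the definitions in 4.1 do not include it. Under section 4.0 the adequacy of skin perfusion is judged by clinical examination in groups 1 to 4 and by fluorescent angiography in groups 5 to 8. The event may therefore differ by arm because of the randomized assessment itself, and no planned rate would show this.

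Third, the power statements describe one binary endpoint where the protocol has three. Section 8.0 says the pilot's estimates will be used to design a larger trial, so a missing any-PRP rate and an unassigned planning rate both bear on the study's stated purpose.

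**Working it through.** **Inputs.** From 5.1 and 8.1.1: eight arms of 20, 160 in all. From 8.3.1: lower rate 10%; two-sided Z test with pooled variance; alpha 0.20 at 20 v 20 and 0.05 at 80 v 80. The documents give no component rates, no any-PRP rate and no overlap, so steps 2 to 4 show ranges under stated assumptions.

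**1. The plan's own figures.** With x1 and x2 events in two groups of n, let p̄ = (x1 + x2)/(2n). Reject when |x1 − x2|/n ÷ √(2p̄(1 − p̄)/n) is at least the two-sided critical value. Power is the sum of the two binomial probabilities' products over the rejection region.

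- 20 v 20, 10% v 40%, alpha 0.20: 0.84713 (plan 0.84713).
- 80 v 80, 10% v 30%, alpha 0.05: 0.90284 (plan 0.90284).
- All nine power rows and all nine actual alphas agree to the printed digits.
- The exact 95% interval for 10/20 is 27.2% to 72.8%, half-width 22.8 points, as stated.

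The arithmetic is sound for a single binary endpoint.

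**2. If each component has a 10% rate.** The any-PRP rate is at least the largest component rate and at most the sum of the three.

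- Full overlap: 10%, or 160 × 0.10 = 16 patients.
- Independent components: 1 − 0.9³ = 27.1%, or 160 × 0.271 = 43.4 patients.
- No overlap: 3 × 10% = 30%, or 160 × 0.30 = 48 patients.

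In one arm of 20 with two patients recorded under each problem, the any-PRP count could be 2 (10%, exact 95% interval 1.2% to 31.7%) or 6 (30%, 11.9% to 54.3%). The three reported rates would be the same in both cases.

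**3. Power over that range,** same test, keeping the plan's difference and moving the lower rate:

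| Lower rate | 80 v 80, +20 points, alpha 0.05 | 20 v 20, +30 points, alpha 0.20 |
|---|---|---|
| 10% | 90.3% | 84.7% |
| 27.1% | 74.9% | 75.8% |
| 30% | 73.1% | 74.2% |

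If 30% were instead the higher of the two rates and 10% the lower, the plan's 90.3% would apply unchanged. The loss arises when the lower rate is itself above 10%.

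**4. If 10% is instead the any-PRP rate,** and the components are equally common, each lies between 10%/3 = 3.3% (no overlap) and 10% (full overlap). At 3.3%, an arm of 20 expects 20 × 0.0333 = 0.67 events per component, and the chance of none is (1 − 0.0333)^20 = 51%. For a 10% outcome that chance is 0.9^20 = 12%. Power for the same absolute differences starting from 3.3% would be 98.2% (80 v 80, 20 points) and 92.9% (20 v 20, 30 points).

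**5. Non-placement, by comparing sections.** Tissue loss in 4.1 is a postoperative clinic finding, infection is identified postoperatively, and delayed healing is an opened incision. A decision during surgery not to place the implant meets none of these, yet 5.1 classes it as a PRP. The schedule in 5.0 puts the placement assessment on the day of surgery and the outcome data sheet at weeks 1 to 4 only, so it is not clear that the event is recorded as an outcome.

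**The case against.** The best defence is that the aim speaks of PRPs in the plural, 4.1 names three, and 8.3.1 estimates each with an interval. That is a coherent reading, and it stands to this extent: the incidence of each type is estimated, and only the patient-level incidence of any PRP is missing. It is also true that this is a rate-estimating pilot and that patient-level data are kept, so an any-PRP rate over the three listed problems could be derived later. But its definition, and the handling of non-placement, would then be chosen after the data were seen.

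A reader might infer three stronger things that the documents do not support.

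- **That 10% fits none of the outcomes.** The text leaves it unassigned. It may have been meant for one component or for the composite.
- **That three primary outcomes triple the number of primary contrasts.** Section 8.3.1 plans estimation. It specifies no set of comparisons with group 1, no decision rule and no error-rate claim, and its second table pools groups into 80 v 80.
- **That non-placement belongs in one composite to which the 10% then attaches.** Nothing supports 10% for such a composite. The decision depends on the randomized assessment and comes before nitroglycerin and the vacuum dressing, which under 4.0 are applied after implant placement. Folding it in without a separate analysis could mask or reverse an effect of angiography and would dilute the other two contrasts.

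**Conclusion.** The point holds in a limited form and is worth correcting. The plan estimates three component incidences but not the share of patients with any PRP, which those rates cannot supply without their overlap. It declares non-placement a PRP and then counts it nowhere. It states power from a 10% rate without naming the outcome.

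If each component is 10%, any-PRP lies between 10% and 30% (16 to 48 of 160). Power for a 20-point increase is then about 90% to 73% with 80 per group, and for a 30-point increase about 85% to 74% with 20 per group. These ranges rest on equal component rates, on unknown overlap, and on the any-PRP rate being the lower of the two rates compared. That the components can co-occur is inferred from their definitions; the documents do not say so. The power tables are not miscalculated. The consequence is for how they can be read and for the planning rates the pilot passes to the next trial.

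**What to change.** 1. In 4.1 and 8.3.1, add a patient-level any-PRP rate by day 30 (at least one of the three listed problems), per arm, with an exact 95% interval. Keep the three component rates beside it.
2. Record non-placement for perfusion reasons. Report it per arm with its own 95% interval, over all randomized patients, including those for whom a replacement envelope is added. Show any-PRP both with and without it.
3. Reconcile 4.1 with 5.1 on whether non-placement is a primary PRP, before outcomes are analysed.
4. In 8.3.1, name the outcome that the 10% and both power tables describe, and settle whether 10% is the eight-group average or the group 1 rate. Show power over the plausible any-PRP range; do not simply relabel 10% as the composite rate.

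The cost is wording in two sections, one derived yes/no variable from the weekly data sheets, and one day-of-surgery item if placement is not already captured. The small downside is that a composite mixes problems of different severity, which the component rates reveal.

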4.2 Secondary Outcomes

4.2.1 The secondary outcomes will be the following:

- Rate of operative intervention secondary to perfusion related problems as listed in "Primary Outcomes" above, and surgical outcome with regards to mastectomy flaps
- Rate of prescribing of outpatient antibiotics or admission for inpatient IV antibiotics for treatment of surgical site infection

The Effect of Nitroglycerin Ointment, Fluorescent Angiography, and Incisional NPWT on Mastectomy Skin Flap Perfusion-Related Problems Comprehensive Cancer Center of Wake Forest University (CCCWFU)

PI: [name] IRB #00038262 NCT03716050 Date of Document: 05/07/2019

- Wound care management modalities for treatment of delayed wound healing complications as listed in “Primary Outcomes” above, and wound healing outcomes

5.0 Treatment Plan

	Pre-Operative Visit	Day of Surgery	Week 1 Postop	Week 2 Postop	Week 3 Postop	Week 4 Postop
Enrollment and informed consent	X					
Clinical assessment to determine whether implant/tissue expander can be placed without compromising perfusion		X				
Clinical photos of surgical site	X	X	X	X	X	X
Data sheet documenting outcome			X	X	X	X

5.1 Study Related Activities

Potential subjects will be identified by the physician, advanced practice provider, or research coordinator. This individual will discuss the study with the patient and answer any questions or concerns they may have. This will take place in an exam room, hospital room, or by phone depending on whether or not the patient is inpatient or a clinic patient.

Signed informed consent will be obtained from each subject who will be undergoing mastectomy with immediate breast reconstruction using breast implants during a pre-operative appointment in the General Surgery (Breast Oncology) or Plastic Surgery clinic. After the subject has been identified as meeting the inclusion criteria by the clinician or research coordinator, the study coordinator will obtain the signed informed consent. A signed copy of the consent form will be given to the subject. Once the patient has agreed to take part in the study and sign the consent form, pre-operative photos of the breast will be taken. Pregnancy tests performed 15 days apart (prior to surgery) is done as standard of care for all women of childbearing age potentially undergoing this surgery.

Twenty subjects will be randomized to each arm of the study using sealed instructions provided by the study coordinator who will inform the clinician of the arm prior to surgery. The envelopes will be filled prior to the study with envelopes containing a document indicating to which group the patient will be a part of. The envelopes will be sealed and shuffled and then labeled from subject 1 through 160.

Once the subject is randomized to an arm of the study, the operating surgeon will be informed of the arm prior to the surgery. On the day of surgery, the surgeon will decide intraoperatively whether an implant/tissue expander can be safely placed without compromising perfusion of the flap. If the surgeon determines that an implant/tissue expander cannot be safely placed, they will continue to be followed as that indicates a perfusion related problem. At that point, another envelope will be introduced into the pre-made envelopes with that subject’s assigned arm. Pictures will be take pre-

The Effect of Nitroglycerin Ointment, Fluorescent Angiography, and Incisional NPWT on Mastectomy Skin Flap Perfusion-Related Problems Comprehensive Cancer Center of Wake Forest University (CCCWFU)

PI: [name] IRB #00038262 NCT03716050 Date of Document: 05/07/2019
operatively, intraoperatively, and at week 1,2,3, and 4 post-operatively. In addition to these pictures, the data collecting sheet will be completed by the physician, advanced practice provider or study coordinator at week 1, 2,3 and 4 post-operatively.

This is not an intent-to-treat trial. In order to ensure that we are able to gather the most information from this study, we want to be able to closely monitor our enrolled subjects and remove any subjects that are non-compliant with their randomized arm. The study coordinator will be responsible for keeping a detailed Excel spreadsheet of the enrolled subjects and their respective arms of the study. If a subject comes off the study prematurely, another envelope will be introduced to the pre-made envelopes with the withdrawn subject's arm – in this way the arms will never be unbalanced.

This study will be monitored by the Cancer Center's Safety and Toxicity Review (STRC) for SAEs and will also be monitored for accrual by the Clinical Research Oversight Committee (CROC) since this is an institutional intervention study. The standard operating procedures for the STRC can be found below in appendix c.

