4.0 Study Outcomes and Study Measures

We will perform a randomized pilot study comprised of eight groups. All of these groups employ accepted techniques, medications and dressings and therefore are not experimental.

Group 1: Breast skin after mastectomy will be clinically examined by the surgeon to determine if there is adequate blood flow to the skin to allow safe coverage of the breast implant. No dye study, ointment, or vacuum dressing will be applied to the breast after implant placement.

Group 2 - Breast skin after mastectomy will be clinically examined by the surgeon, and nitroglycerin (NTG) cream will be applied to the breast skin after implant placement. This cream does not have systemic effects but may improve blood flow to the remnant breast skin after mastectomy.

Group 3 - Breast skin after mastectomy will be clinically examined by the surgeon, and an incisional vacuum-assisted dressing (iVAC) will be placed over the breast incisions after implant placement, which may improve blood flow to the skin and help wound healing.

Group 4 - Breast skin after mastectomy will be clinically examined by the surgeon, and both NTG cream will be applied to the breast skin and an iVAC will be placed over the incisions after implant placement.

Group 5 - Blood flow to breast skin after mastectomy will be examined using a fluorescent dye study called fluorescent angiography (FA) to determine if there is adequate blood flow to the skin to allow safe coverage of the breast implant. No further intervention will be used after implant placement.

Group 6 - Blood flow to breast skin breast skin will be examined using FA, and NTG cream will be applied to the skin after the implant is placed.

Group 7 - Blood flow to breast skin breast skin will be examined using FA, and an iVAC will be placed over breast skin incisions after the implant is placed.

Group 8 - Blood flow to breast skin breast skin will be examined using FA, and both NTG cream and iVAC will be used as interventions after the implant is placed.

The dosage of indocyanine-green (IC-green) to be used for assessment of mastectomy flaps will be in 10 mg boluses, not to exceed 5 mg/kg.

Nitro-Bid® (nitroglycerin ointment, 2%) at a dose of 45 mg (equal to 7.5 cm on the measuring strip provided with packaging) will be used. The paste will be applied to remnant breast skin after skin closure and surgical dressings placed over top.

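### The surgeon is told the whole arm before surgery, so the implant decision is made knowing whether nitroglycerin or the vacuum dressing will follow; this can bias comparisons of arms with such a back-up against arms with none

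*Combined protocol and SAP*

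**What the plan says.** Section 5.1 discloses the allocation before surgery in two places. Randomisation uses "sealed instructions provided by the study coordinator who will inform the clinician of the arm prior to surgery". Later in the section, "the operating surgeon will be informed of the arm prior to the surgery". The arms are the eight groups of Section 4.0, each a combination of FA yes/no, NTG yes/no and iVAC yes/no, so knowing the arm means knowing all three.

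After that disclosure, on the day of surgery, "the surgeon will decide intraoperatively whether an implant/tissue expander can be safely placed without compromising perfusion of the flap". Of patients in whom placement is judged unsafe, Section 5.1 says "they will continue to be followed as that indicates a perfusion related problem", and it adds a further envelope for the same arm.

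Section 4.0 puts the other two treatments later. For NTG: "The paste will be applied to remnant breast skin after skin closure and surgical dressings placed over top". For iVAC, in Group 3: "an incisional vacuum-assisted dressing (iVAC) will be placed over the breast incisions after implant placement". Group 8 follows the same order: "both NTG cream and iVAC will be used as interventions after the implant is placed".

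The documents contain no staged disclosure, no masking of the surgeon and no objective threshold for the placement decision.

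**The concern.** FA has to be known in theatre because it informs the placement decision. NTG and iVAC status does not, and the documents give no reason for disclosing it early. Section 4.0 says that NTG and iVAC may each improve blood flow to the skin. A surgeon facing a marginal flap who knows that one or both will follow thus has a reason, found in the protocol itself, to judge that flap differently from one in Group 1 or 5, where nothing will follow.

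If that happens, patients who receive an implant differ between arms for a reason other than the treatment. The decision comes after randomisation and is made with knowledge of the arm, so later adjustment cannot reliably separate its influence from a treatment effect. Better concealment at enrolment, or masking of the weekly assessors, would not remove this route: the surgeon would still know the NTG and iVAC assignment when deciding.

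At stake are the between-arm comparisons in Section 8.3 and the rates that Section 8.0 intends to use in designing a larger trial.

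**Working it through.** **Order of events.** (1) The full arm is disclosed (5.1). (2) FA or clinical examination of the flap (4.0). (3) Placement decision (5.1). (4) NTG after skin closure; iVAC over the incisions after implant placement (4.0). Only the FA component is used by step 3.

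**Which comparisons are exposed.** With 20 per group, the arms with NTG and/or iVAC are Groups 2, 3, 4, 6, 7 and 8: 6 × 20 = 120 subjects. Groups 1 and 5 have neither: 2 × 20 = 40.

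- Groups 2–4 v Group 1, and Groups 6–8 v Group 5: back-up against none, fully exposed.
- Group 2 v 3 and Group 6 v 7: a back-up on both sides, so this route does not separate them.
- FA yes/no at the same NTG and iVAC status: not affected by this route.
- Pooled NTG yes/no (80 v 80): the NTG side is Groups 2, 4, 6 and 8. The comparator is Groups 1, 3, 5 and 7, of which Groups 3 and 7 (40 of 80) have iVAC. Pooled iVAC yes/no is the mirror image.

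**Dilution.** Let d be the shift in recorded event rate caused by knowing that any back-up will follow. In the pooled NTG comparison, the NTG side shifts by d and the comparator by (40 × d + 40 × 0)/80 = d/2. The net bias is d − d/2 = d/2, so a net 5 points needs d = 10 points. If knowing NTG and knowing iVAC instead had separate additive effects, the iVAC part would cancel and there would be no halving.

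**Per-case sensitivity.** One changed recorded outcome moves an arm of 20 by 1/20 = 5 points. In a group of 80, four are needed: 4/80 = 5 points, half of the 10% planning rate.

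**The plan's own figure.** Exact enumeration of the two-sided pooled z test gives 0.9028 for 10% v 30%, 80 v 80, alpha 0.05 (Section 8.3: 0.90284). It gives 0.8471 for 10% v 40%, 20 v 20, alpha 0.20 (Section 8.3: 0.84713). The method reproduces the plan.

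**What an assumed bias would do.** The documents give no frequency of altered decisions, so every d below is an assumption. Suppose there is no true treatment effect and the rate is 10% without a back-up and 10% + d with one. The diluted column takes Binomial(80, 0.10 + d) against Binomial(40, 0.10) + Binomial(40, 0.10 + d). The undiluted column takes 10% + d against 10%. Entries are chances of a significant result.

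| d (points) | 20 v 20, alpha 0.20 | 80 v 80, alpha 0.05, diluted | 80 v 80, alpha 0.05, undiluted |
|---|---|---|---|
| 0 | 22.7% | 4.9% | 4.9% |
| 5 | 26.4% | 7.2% | 15.6% |
| 10 | 36.5% | 12.8% | 42.3% |
| 15 | 49.4% | 21.1% | 71.6% |

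In the other direction, a true 10% v 30% difference masked by a net 5 or 10 points becomes 10% v 25% or 10% v 20%. Section 8.3's own rows then show power falling from 90.3% to 71.6% or 42.3%.

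**Direction.** Section 5.1 calls non-placement a perfusion-related problem; Section 4.1 does not list it among the primary outcomes. Suppose surgeons are more cautious in Groups 1 and 5.

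- If non-placement counts as an event, events collect in those groups and the treatments look better than they are.
- If it does not count, marginal flaps drop out of those groups, replacements are added, and the treatments look worse.

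Suppose instead that surgeons accept more marginal flaps where a back-up is assigned. Non-placements there fall, but later tissue loss may rise; if both count, the two pull against each other.

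**The case against.** The case against has real force on scope and size.

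- A reader might infer that every NTG and iVAC comparison is biased. The documents do not support that: Groups 2 v 3 and 6 v 7 have a back-up on both sides, and the pooled comparisons are diluted if what matters is having any back-up.
- A reader might infer that each altered placement decision moves an arm by 5 points. It does so only if the decision, or a later event that it causes, enters the count. Whether non-placement counts is unsettled.
- A reader might extend the mechanism to flap tension or flap handling in general. The documents describe one decision, placement of an implant or expander judged on perfusion; anything further is inference.
- Section 4.0 says the arm never takes priority over the subject's health. That limits departures from good judgement, but without a stated threshold it does not make judgement of a marginal flap the same across arms.
- The trial is a pilot, and much of the output is rates with confidence intervals. This lowers the weight but does not remove the point: Section 2.0 aims to compare the interventions, Section 8.3 gives power for between-group and pooled comparisons, and Section 8.0 carries the rates forward.

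Two further objections do not stand. That surgeons cannot be blinded is beside the point, since only later disclosure of two components is asked for. Safety is not a barrier either, since contraindications to NTG and iVAC are screened at eligibility (Section 3.2).

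**Conclusion.** The point holds as an avoidable route for performance bias. It is certain that the whole arm is disclosed before a subjective placement decision and that NTG and iVAC status is not needed for that decision. It is not established that surgeons would decide differently, or which way the results would move.

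The bias can reach comparisons of back-up arms with Groups 1 and 5 and the pooled NTG and iVAC comparisons. In the latter it is halved if any back-up has one common effect, and not halved if the two have separate effects. The only sizes that the documents support are sensitivities: 5 points per changed recorded outcome in an arm of 20, and 5 points per four changed outcomes in a group of 80. The error rates tabulated above rest on assumed shifts and are not evidence that a bias of that size would occur.

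The change is worth making because it is cheap and the bias cannot be reliably undone at analysis.

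**What to change.** In Section 5.1, split each sealed allocation into two parts. Part A (FA yes/no) is opened before surgery. Part B (NTG yes/no, iVAC yes/no) is opened in the operating room only after the placement decision has been recorded and the skin closed.

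Amend both disclosure sentences, the one about the coordinator informing the clinician and the one about the operating surgeon, so that each refers to the FA allocation only. Changing one alone would leave the section contradicting itself and could still reveal the full arm. Prepare replacement envelopes in the same two parts. State what happens to Part B when no implant is placed, and reconcile Sections 4.1 and 5.1 on whether non-placement counts as an outcome event.

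The cost is protocol wording, a second envelope per subject, and having NTG and iVAC supplies at hand for every case until Part B is opened. No extra patients or visits are needed, and no dose or clinical rule changes.
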